10.5.4. Clinical Laboratory Assessments

Details regarding clinical laboratory sample collection, preparation, and shipment are provided in the laboratory manual by the central laboratory. All laboratory assessments required by the protocol will be performed by a central laboratory unless otherwise stated. Refer to [Table 5](#) for the list of clinical laboratory tests to be performed and the Schedules of Assessments ([Appendix 1](#) and [Appendix 2](#)) for timing and frequency for each test.

Clinical safety laboratory tests should be completed predose. The Investigator must review the laboratory report, document the review, and record any clinically relevant changes on the AE section of the eCRF (results of the white blood cell differential and ALC will be reviewed and monitored as described in [Section 10.5.7.2](#)). The laboratory reports must be filed with the source documents.

All laboratory tests with values considered clinically significantly abnormal during participation in the study or within 30 days after the last dose of study drug should be repeated until the values return to normal or Baseline or are no longer considered clinically significant by the Investigator. If such values do not return to normal or Baseline, or otherwise resolve to a nonclinically significant value within a reasonable period of time, as judged by the Investigator, the etiology should be identified, and the Medical Monitor should be notified. In cases when laboratory values from non-protocol-specified assessments are performed at the institution's local laboratory and result in a change in subject management or are considered clinically significant by the Investigator (eg, AE or dose modification), then the results must be recorded in the eCRF.

Information on the grading and management of laboratory abnormalities according to assessed severity is provided in [Appendix 4](#) and [Appendix 5](#).

Table 5: Clinical Laboratory Tests

Infectious Disease HBsAg, HCV antibody (with reflex PCR), HIV, TB^a
	
Drugs of Abuse Urine drug screen: amphetamine, barbiturates, benzodiazepines, cocaine metabolites, opiates
												

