10.5.7. Safety Monitoring Guidance

10.5.7.1. Drug-Induced Liver Injury

Based on US FDA guidance for drug-induced liver injury ([FDA 2009](#)), discontinuation of study drug should be considered if any of the following occur:

- ALT or AST $> 8 \times$ ULN
- ALT or AST $> 5 \times$ ULN for > 2 weeks
- ALT or AST $> 3 \times$ ULN AND Total Bilirubin $> 2 \times$ ULN, or international normalized ratio > 1.5
- ALT or AST $> 3 \times$ ULN with the appearance of fatigue, nausea, vomiting, right upper quadrant pain or tenderness, fever, rash, and/or eosinophilia ($> 5\%$)

Information on the grading and management of laboratory abnormalities according to assessed severity is provided in [Appendix 4](#) and [Appendix 5](#).

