4.3 Windowing Conventions

When available, visits will be analyzed as scheduled (refer to protocol Appendices 1 and 2). ET and/or unscheduled/retest measurements will only be included if a scheduled measurement is not available, and the ET or unscheduled/retest measurement falls within the analysis visit windows as described in [Table 1](#).

If there is more than one retest, unscheduled or ET assessment for a given analysis visit, the assessment closest to the target day will be retained for data summary of that visit; if there are 2

observations with equal distance to the target day, then the later one will be retained. All data from scheduled, retest, unscheduled, and ET visit assessments will be listed.

Table 1: Analysis Visit Windows

Analysis Visit	Target Study Day	Visit Window (Period Day)
DB Treatment Period		
DB Baseline	1	Refer to DB Treatment Period Baseline definition in Section 4.1
Week 1 (Cohort 2 only)	Day 8	Post first dose – Day 11
Week 2	Day 15	Cohort 1: Post first dose – Day 21 Cohort 2: Day 12 – Day 21
Week 4	Day 29	Day 22 – Day 42
Week 8	Day 57	Day 43 – Day 70
Week 12	Day 85	Day 71 – Day 98
Week 16	Day 113	Day 99 – Day 126
Week 20	Day 141	Day 127– Day 154
Week 24*	Day 169	Day 155 – (Last treatment day + 6) in DB period for subjects never treated in OLE; Day 155 – Pre first dose in OLE for subjects treated in OLE
OLE Period **		
OLE Baseline	OLE Day 1	Refer to OLE Period Baseline definition in Section 4.1
Week 25	OLE Day 8	Post first dose in OLE – OLE Day 18
Week 28	OLE Day 29	OLE Day 19 – OLE Day 56
Week 36	OLE Day 85	OLE Day 57 – OLE Day 112
Week 44	OLE Day 141	OLE Day 113 – OLE Day 168
Week 52	OLE Day 197	OLE Day 169 – (Last treatment day + 6)
Safety Follow-up 1	Last treatment day + 14 days (± 3 days)	(Last treatment day + 7) – (Last treatment day + 21 days)
Safety Follow-up 2	Last treatment day + 28 days (± 3 days)	(Last treatment day + 22 days) - (Last contact day)

DB = Double-Blind; OLE = Open-Label Extension; SFU = Safety Follow-Up

* Week 24 is the last scheduled visit in DB Treatment Period and first scheduled visit in OLE Period.

** The days are Period Day (refer to Section 4.2) in the OLE Period.

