4.5 Handling of Retests, Unscheduled Visits, and Early Termination Data

Retests measurements, unscheduled measurements, and ET visit assessments will be included in analysis and summarized via analysis visit windowing according to the windowing conventions in Section 4.3.

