11.2 Clinical Laboratory

For quantitative laboratory test, descriptive statistics will be presented for data related to chemistry, hematology (including coagulation) and quantitative urinalysis. Observed values and change from baseline values will be presented for each post-baseline visit. Frequencies and percentages of subjects in each result category will be provided for qualitative urinalysis data.

Shift tables from baseline to each post-baseline visits describing shifts to abnormality (low or high) will be provided as well. Only subjects with a baseline result and a result at the specified visit for the parameter will be considered.

Separate listings of all data for chemistry, hematology (including coagulation), urinalysis and pregnancy test will be provided.

In addition, separate listings of data for chemistry, hematology (including coagulation), and urinalysis will be provided for each parameter where a subject had at least one abnormal result.

Incidence of hepatic enzyme elevations will be summarized by visit. The following hepatic enzyme elevations will be reported:

- ALT > 1, >2, > 3, > 5, > 8, > 10, and > 20 x upper limit of normal (ULN)
- AST > 1, > 2, > 3, > 5, > 8, > 10, and > 20 x ULN
- ALT or AST > 3, > 5, > 10, and > 20 x ULN
- ALP > 1, > 1.5, > 2, > 3, > 5, > 8, > 10, and > 20 x ULN
- GGT > 1, > 2, > 3, > 5, > 8, > 10, and > 20 x ULN
- Total bilirubin >1, > 1.5, >2, and >3 x ULN
- ALT or AST > 3 x ULN AND total bilirubin > 1.5 x ULN
- ALT or AST > 3 x ULN AND total bilirubin > 2 x ULN
- ALT or AST > 3 x ULN AND ALP > 1.5 x ULN
- Symptomatic elevation in ALT or AST, defined as an ALT or AST elevation > 3 x ULN in temporal association with nausea, vomiting, anorexia, abdominal pain, or fatigue, where temporal association is defined as onset of symptoms within +/- 14 days of the elevation.

Incidence of absolute lymphocyte count decrease at any time during a study period (post-dose on Day 1 to pre-dose on Week 24 for the DB Treatment Period and post-dose on Week 24 to the 2nd SFU visit for the OLE Period) will be summarized. The following categories will be presented:

- Grade 1, defined as an absolute lymphocyte count ≥ 0.8 to $< 1.02 \times 10^9/L$
- Grade 2, defined as an absolute lymphocyte count ≥ 0.5 to $< 0.8 \times 10^9/L$
- Grade 3, defined as an absolute lymphocyte count ≥ 0.2 to $< 0.5 \times 10^9/L$

- Grade 4, defined as an absolute lymphocyte count ≥ 0.0 to $< 0.2 \times 10^9/L$
- Any Grade 3 or 4
- Any Grade 1 to 4

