Table 14.3.1.6.1	Summary of Serious Treatment Emergent Adverse Events by System Organ Class and Preferred Term – Double-Blind Treatment Period (Safety Set)
Table 14.3.1.7.1	Summary of Treatment Emergent Adverse Events of Special Interest by Category and Preferred Term - Double-Blind Treatment Period (Safety Set)
Table 14.3.2.4	Listing of Treatment Emergent Adverse Events Leading to Study Discontinuation (Safety Set)
Table 14.3.4.12.1	Incidence of Hepatic Enzyme Elevations by Visit - Double-Blind Treatment Period (Safety Set)
Table 14.3.4.13.1	Incidence of Absolute Lymphocyte Count Decrease - Double-Blind Treatment Period (Safety Set)
Table 14.3.5.2	Summary of Vital Signs Cardiac Monitoring I - Full Study (Safety Set)

Primary Analysis – Batch 2

Table Number	Table Title
Table 14.1.1.0	Study Information
Table 14.1.1.1.1	Subject Disposition - Screening (All Subjects)
Table 14.1.1.2.1	Analysis Sets – Double-Blind Treatment Period (Randomized Set)
Table 14.1.2.1	Demographic and Baseline Characteristics - Double-Blind Treatment Period (Randomized Set)
Table 14.1.2.3	Demographic and Baseline Characteristics - Double-Blind Treatment Period (Safety Set)
Table 14.1.3.1.1	Important Protocol Deviations - Double-Blind Treatment Period (Randomized Set)
Table 14.1.3.2.1.1	Major Protocol Deviations - Double-Blind Treatment Period (Randomized Set)
Table 14.1.3.2.1.2	Major Protocol Deviations Leading to the Exclusion from the Per Protocol Set - Double-Blind Treatment Period (Randomized Set)
Table 14.1.3.3.1	Protocol Deviations Associated to COVID-19 - Double-Blind Treatment Period (Randomized Set)
Table 14.1.4.1	Surgical and Medical History (Safety Set)
Table 14.1.4.2.1	Alopecia Areata Disease History (Safety Set)
Table 14.1.4.2.2	Alopecia Areata Disease History (Full Analysis Set)
Table 14.1.5	Prior Medications - Double-Blind Treatment Period (Safety Set)
Table 14.1.6.1	Concomitant Medications - Double-Blind Treatment Period (Safety Set)
Table 14.1.7.1	Study Treatment Exposure and Compliance - Double-Blind Treatment Period (Safety Set)
Table 14.2.1.3.2	Subgroup Analysis: Summary of SALT I Score - Observed Cases - Double-Blind Treatment Period - Sex (Full Analysis Set)
Table 14.2.1.3.3	Subgroup Analysis: Summary of SALT I Score - Observed Cases - Double-Blind Treatment Period - Race (Full Analysis Set)
Table 14.2.1.3.4	Subgroup Analysis: Summary of SALT I Score - Observed Cases - Double-Blind Treatment Period - Age (Full Analysis Set)

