Table 14.3.4.4.2	Summary of Qualitative Urinalysis Laboratory Assessments - Open-Label Extension Period (Open-Label Extension Safety Set)
Table 14.3.4.5.2	Shift from Baseline for Chemistry Laboratory Assessments - Open-Label Extension Period (Open-Label Extension Safety Set)
Table 14.3.4.6.2	Shift from Baseline for Hematology Laboratory Assessments - Open-Label Extension Period (Open-Label Extension Safety Set)
Table 14.3.4.7.2	Shift from Baseline for Quantitative Urinalysis Laboratory Assessments - Open-Label Extension Period (Open-Label Extension Safety Set)
Table 14.3.4.8.2	Shift from Baseline for Qualitative Urinalysis Laboratory Assessments - Open-Label Extension Period (Open-Label Extension Safety Set)
Table 14.3.4.9	Listing of Abnormal Chemistry Laboratory Assessments (Safety Set)
Table 14.3.4.10	Listing of Abnormal Hematology Laboratory Assessments (Safety Set)
Table 14.3.4.11	Listing of Abnormal Urinalysis Laboratory Assessments (Safety Set)
Table 14.3.4.12.2	Incidence of Hepatic Enzyme Elevations by Visit - Open-Label Extension Period (Open-Label Extension Safety Set)
Table 14.3.4.13.2	Incidence of Absolute Lymphocyte Count Decrease - Open-Label Extension Period (Open-Label Extension Safety Set)
Table 14.3.5.1.2	Summary of Vital Signs - Open-Label Extension Period (Open-Label Extension Safety Set)
Table 14.3.5.2	Summary of Vital Signs Cardiac Monitoring I – Full Study (Safety Set)

Table Number	Table Title
Table 14.3.5.3	Summary of Vital Signs Cardiac Monitoring II – Full Study (Safety Set)
Table 14.3.6.1.2	Summary of ECG Evaluations - Open-Label Extension Period (Open-Label Extension Safety Set)
Table 14.3.6.1.3.1	Summary of ECG Cardiac Monitoring I – Full Study (Safety Set)
Table 14.3.6.1.3.2	Summary of ECG Cardiac Monitoring II – Full Study (Safety Set)
Table 14.3.6.2.2	Summary of Outliers of ECG QTcF Interval - Open-Label Extension Period (Open-Label Extension Safety Set, Subjects with No QTcF Outlier Value at Pre-Dose Week 24)
Table 14.3.7.1.2	Summary of Value and Change from Baseline in Pulmonary Function Tests - Open-Label Extension Period (Open-Label Extension Safety Set)
Table 14.3.7.2.2	Incidence of Markedly Abnormal and/or Potentially Important Pulmonary Function Test Values by Visit - Open-Label Extension Period (Open-Label Extension Safety Set)
Table 14.3.7.3.2	Shift from Baseline in Overall Interpretation of Pulmonary Function Tests - Open-Label Extension Period (Open-Label Extension Safety Set)

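### Liver enzyme elevations are tabulated by visit only, from one selected value per window, so peaks found on on-treatment retests are left out and no any-time count is given

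*SAP*

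**What the plan says.** SAP 11.2 lists multiples of the upper limit of normal (ULN) for ALT, AST, ALP, GGT and total bilirubin, with several combined criteria, and states: "Incidence of hepatic enzyme elevations will be summarized by visit". No worst-value or any-time row is specified. Both planned tables, 14.3.4.12.1 for the double-blind period and 14.3.4.12.2 for the open-label extension, are titled by visit in SAP Appendix 3.

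SAP 4.3 decides which value represents a visit: "ET and/or unscheduled/retest measurements will only be included if a scheduled measurement is not available", and the value must also fall inside the analysis window. If several such values compete for a window, "the assessment closest to the target day will be retained for data summary of that visit". The choice depends on timing, not on the height of the result. SAP 4.5 says that retest, unscheduled and early-termination values are included, but only as "summarized via analysis visit windowing according to the windowing conventions in Section 4.3". Neither section makes an exception for liver tests.

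Protocol 10.5.4 says that clinically significant abnormal laboratory values "should be repeated until the values return to normal or Baseline or are no longer considered clinically significant". Protocol Appendix 5 adds that clinically significant Grade 3 and Grade 4 laboratory abnormalities are confirmed within 3 calendar days of receiving the result.

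**The concern.** The protocol asks for repeat tests when a result is worrying, and the SAP's selection rule sets those repeats aside whenever the visit already has its routine sample. The excluded values therefore come mainly from subjects who are being followed for an abnormality.

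Incidence and severity of laboratory abnormalities is a named safety endpoint (Protocol 11.9.1; SAP 2.2.1.4 and 2.2.2.2). For liver tests, the usual questions are how many subjects per arm ever passed each threshold and how high they went. A by-visit table built on one selected value per window answers neither with certainty.

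**Working it through.** The plan states no figure to reproduce here. The check applies the selection rule to the visit schedule.

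**Step 1: are the windows continuous?** From SAP Table 1, double-blind: Day 22-42, 43-70, 71-98, 99-126, 127-154, then from Day 155. Open-label: Day 19-56, 57-112, 113-168, then from Day 169 to last treatment day + 6. Each window starts the day after the previous one ends, so any on-treatment retest falls in a window.

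**Step 2: does each window hold a scheduled chemistry value?** Protocol Appendices 1 and 2 schedule laboratory tests at every post-baseline treatment visit. Safety Follow-Up 1 is different: only hematology is scheduled there in both cohorts. For a subject with no missed treatment visit, every on-treatment window is occupied and every on-treatment retest is excluded. In the Safety Follow-Up 1 window (last treatment day + 7 to + 21) a chemistry retest can still be counted.

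**Step 3: how long does one value stand for?** Length = last day - first day + 1.
- Weeks 8, 12, 16 and 20: for example 70 - 43 + 1 = 28 days each
- Week 28: 56 - 19 + 1 = 38 days
- Weeks 36 and 44: 112 - 57 + 1 = 56 days each

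**Step 4: a hypothetical subject (assumed values).** ALT is 4 x ULN at the scheduled Week 8 visit (Day 57), 9 x ULN on a Day 60 retest, 5.5 x ULN on a Day 67 retest, and 1 x ULN at the scheduled Week 12 visit (Day 85). SAP 4.3 keeps 4 for Week 8 and 1 for Week 12.

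| ALT row | By visit under SAP 4.3 | Any time, all values |
|---|---|---|
| > 1, > 2, > 3 x ULN | counted | counted |
| > 5 x ULN | not counted | counted |
| > 8 x ULN | not counted | counted |
| > 10, > 20 x ULN | not counted | not counted |

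The combined rows behave the same way. If bilirubin is below its limit on Day 57 and passes 2 x ULN only on Day 60, the ALT-with-bilirubin row misses the subject.

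**Step 5: early-termination values.** The same rule applies. Suppose the scheduled Week 8 sample is on Day 57, the last dose on Day 60 and the early-termination visit on Day 64. Day 64 lies in the occupied Day 43-70 window, so that sample is not used in the table.

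**Step 6: direction.** The selected values are a subset of all values. The number of subjects above a threshold on selected values can equal the any-time number or fall below it, but cannot exceed it.

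**Step 7: ever-exceeded counts.** Take one subject above 3 x ULN at Week 8 and another at Week 12. The by-visit table shows one and one. A single subject elevated at both visits gives the same table. This holds even if nobody is retested.

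**Step 8: size of one case.** Planned double-blind arms are 24 on 3 mg, 24 + 6 = 30 on 2 mg, and 12 + 12 = 24 on placebo. One subject is 1/24 = 4.2 or 1/30 = 3.3 percentage points. The plan does not give the sizes of the open-label dose groups, so these percentages do not carry over to the extension.

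**The case against.** The strongest reply is that nothing disappears from the report. SAP 4.3 lists all retest and unscheduled data, and SAP 11.2 adds a listing for each chemistry parameter with an abnormal result (Table 14.3.4.9). With about 78 subjects, a reader can find each peak. Protocol 10.5.4 also has clinically relevant changes recorded as adverse events, and SAP 11.1 summarizes these by maximum severity. This stands, and it limits the point to two descriptive tables. It does not remove it: the adverse-event route depends on the investigator's judgement, and Grade 3 in Protocol Appendix 4 runs from > 5 to 20 x ULN (normal baseline), so it cannot separate the > 5, > 8 and > 10 rows.

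Several stronger readings are tempting but not supported:
- **That all unscheduled values are lost.** They are used when the scheduled value is missing, and a chemistry retest in the Safety Follow-Up 1 window can count.
- **That every threshold count is pulled towards zero.** A repeat is often prompted by a scheduled value that is already raised, and that subject still counts at the lower levels. What is at risk is mainly the higher category.
- **That peaks will usually be found on retests.** The documents give no rate, and Protocol 1.2 reports no notable concern with laboratory results. In the example above, 4 x ULN is Grade 2 with a normal baseline, so its retest would rest on the investigator judging the value clinically significant.
- **That the SAP must tabulate ALT or AST with INR because Protocol 10.5.7.1 names it.** That section lists triggers for considering discontinuation of study drug and is not an analysis specification. Coagulation results are summarized separately.
- **That the SAP's other any-time counts already include retests.** Lymphocytes (11.2), pulmonary function (11.6) and foveal thickness (11.7) show that the format is in use, but none says in terms that SAP 4.3 is set aside.

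**Conclusion.** The point holds for the incidence tables. As written, they can understate the highest liver category reached on treatment, including combined criteria met only on a repeat draw, and they do not report how many subjects ever exceeded a threshold.

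The exclusion of on-treatment retests is complete for a subject with every scheduled chemistry value present, and partial otherwise. One missed case would be 3.3 to 4.2 percentage points of a planned double-blind arm. How many cases would be missed cannot be estimated, because the documents give no rate of elevation or retesting. The conclusion rests on reading SAP 4.3 and 4.5 as governing Tables 14.3.4.12.1 and 14.3.4.12.2, which the text supports and no exception contradicts. It affects no efficacy result, and the underlying values remain available. It is worth changing because the remedy is nearly free.

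**What to change.** In SAP 11.2, and in both tables, keep the by-visit rows and add for each listed criterion one row per study period: any time post-baseline, worst value. State that it uses all scheduled, retest, unscheduled, early-termination and follow-up values, and that the one-value-per-window selection in SAP 4.3 does not apply to it.

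Bound each row by period dates, as SAP 11.2 already does for lymphocyte counts (post-dose Day 1 to pre-dose Week 24; post-dose Week 24 to the second follow-up visit), and assign the follow-up values of subjects who never enter the extension to the double-blind period. This matters because SAP 4.1 sets the extension baseline back to the double-blind baseline for subjects already on etrasimod, so post-baseline alone would not confine the extension row to the extension.

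The cost is a few sentences of SAP text and extra rows in two planned tables, with no new data. A row for ALT or AST with INR, and a fixed interval for pairing the two parts of a combined criterion, are optional and not needed to close this point.

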11.3 Vital Signs

Descriptive statistics will be presented for data related to vital signs (systolic blood pressure, diastolic blood pressure, pulse rate, respiratory rate, temperature, and weight). Observed values, and change from baseline values will be presented for each post-baseline assessment.

At nominal Day 1 and Week 24 visits, descriptive statistics for the observed and change from pre-dose measurement in vital signs will be presented at pre-dose (observed values only), 1 hour, 2 hours, 3 hours, and 4 hours after treatment initiation. Frequency count and percentage will also be reported for the following cardiac monitoring categories:

- Heart rate (HR) < 40 bpm at any time during the first 4 hours post-dose
- HR < 50 bpm at any time during the first 4 hours post-dose
- HR < 40 bpm at the 4-hour post-dose timepoint
- HR < 50 bpm at the 4-hour post-dose timepoint

A listing of all vital sign assessments will be provided.

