11.9.1. Safety Endpoints

- Incidence and severity of AEs
- Incidence and severity of laboratory abnormalities and change from Baseline in laboratory values (to include hematology, serum chemistry, coagulation, and urinalysis)
- Incidence of clinically significant vital sign abnormalities and changes from Baseline (may include 4 hours postdose on Day 1 and Week 24)
- ECGs
- Holter Monitoring
- Physical examination findings

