11.9.6. Electrocardiograms and Vital Signs

Individual ECG values will be listed by visit and summarized using descriptive statistics. Parameters to be provided for each ECG are HR and the following intervals: RR, PR, QRS, QT, QTc, and QTcF. Post-Baseline ECGs for each subject will be compared with the Baseline ECG. Any clinically significant change from Baseline may be recorded as an AE if deemed appropriate by the Investigator, or the Investigator in consultation with the Sponsor or delegate. Outlier analysis will be performed on all subjects with QTcF values > 500 ms or change from Baseline > 60 ms in the absence of Baseline ECG abnormalities that preclude accurate surface ECG assessment of ventricular repolarization (eg, bundle branch block).

Descriptive statistics for vital signs (BP, HR, respirations, and body temperature) will be presented by treatment group.

The change from Baseline for each of the vital signs and ECG parameters will be summarized. Incidence of abnormal vital signs parameters and outlier ECG results will be tabulated.

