2.2.1.4 Safety Endpoints

- Incidence and severity of adverse events (AEs) throughout the DB Treatment Period
- Incidence and severity of laboratory abnormalities and change from Baseline in laboratory values (to include hematology, serum chemistry, coagulation, and urinalysis) at Weeks 1 (Cohort 2 only), 2, 4, 8, 12, 16, 20, and 24
- Incidence of clinically significant vital sign abnormalities and changes from Baseline at 1-, 2-, 3-, and 4-hour post-dose on Day 1 as well as Weeks 1 (Cohort 2 only), 2, 4, 8, 12, 16, 20, and 24
- Electrocardiograms (ECG) at 4-hour post-dose on Day 1 as well as Weeks 12 and 24
- Holter Monitoring on Day 1 (Cohort 2 only) and Week 1 (Cohort 2 only)*
- Physical examination findings (abnormalities will be recorded and summarized as medical history or AEs, as applicable)

* The statistical analysis to be performed for these endpoints will be described in a separated SAP (refer to Section 1)

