2.2.2.2 Safety Endpoints

- Incidence and severity of AEs throughout the OLE Period
- Incidence and severity of laboratory abnormalities and change from Baseline in laboratory values (to include hematology, serum chemistry, coagulation, and urinalysis) at Weeks 25, 28, 36, 44, and 52
- Incidence of clinically significant vital sign abnormalities and changes from Baseline at

1-, 2-, 3-, and 4-hour post-dose on Week 24 as well as Weeks 25, 28, 36, 44, and 52

- ECG at 4-hour post-dose on Week 24 as well as Weeks 36, 44, and 52
- Holter Monitoring at Weeks 24 and 25 as well as any time a subject escalates from 2 mg to 3 mg etrasimod*
- Physical examination findings (abnormalities will be recorded and summarized as AEs)

* The statistical analysis to be performed for these endpoints will be described in a separated SAP (refer to Section 1)

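### Incidence of vital sign abnormalities is a listed safety endpoint, but SAP 11.3 counts only low heart rate in the 4 hours after the Day 1 and Week 24 doses; blood pressure has no count

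*SAP*

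**What the plan says.** The protocol makes two statements. Section 11.9.1 lists the endpoint: "Incidence of clinically significant vital sign abnormalities and changes from Baseline (may include 4 hours postdose on Day 1 and Week 24". Section 11.9.6 promises the analysis: "Incidence of abnormal vital signs parameters and outlier ECG results will be tabulated". The synopsis repeats that promise. Neither statement is limited to heart rate, and Section 11.9 leaves the detailed description of safety analyses to the SAP.

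The SAP attaches the endpoint to visits. For the double-blind period, Section 2.2.1.4 gives "Incidence of clinically significant vital sign abnormalities and changes from Baseline at 1-, 2-, 3-, and 4-hour post-dose on Day 1", then Weeks 1 (Cohort 2 only), 2, 4, 8, 12, 16, 20 and 24. For the extension, Section 2.2.2.2 gives the same endpoint at "1-, 2-, 3-, and 4-hour post-dose on Week 24 as well as Weeks 25, 28, 36, 44, and 52".

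SAP 11.3 plans descriptive statistics for six parameters (systolic and diastolic blood pressure, pulse rate, respiratory rate, temperature, weight) and a listing. For the nominal Day 1 and Week 24 visits it adds: "Frequency count and percentage will also be reported for the following cardiac monitoring categories". Four categories follow: heart rate below 40 and below 50 bpm, each at any time in the first 4 hours after the dose and at the 4-hour timepoint.

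**The concern.** The endpoint has two parts, incidence of abnormality and change from baseline. SAP 11.3 covers change from baseline for every parameter. It covers incidence only for low heart rate in two 4-hour windows. The SAP does not say what makes a vital sign abnormality clinically significant and sets no limit for blood pressure, respiratory rate or temperature.

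Safety is part of the primary objective, and the trial exists in its present form to compare 2 mg and 3 mg. If the SAP is followed as written, the report will not state how many subjects in each arm had an abnormal blood pressure at any visit. Nor will it state how many had a low vital-sign heart rate at the later visits, where the 3 mg arm is actually on 3 mg.

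**Working it through.** The plan gives no figure to reproduce on this point. The check sets the endpoint lists against the planned counts, the dosing schedule and the table list.

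1. **Parameters.** SAP 11.3 names 6 parameters. Those with an abnormality count: heart rate only, so 1 of 6. Blood pressure has no count at any visit.

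2. **Visits.** Beyond the two monitored windows, the endpoint lists name these assessments:

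| Period | Listed assessments outside the 4-hour windows | Number | With a count |
|---|---|---|---|
| Double-blind | Weeks 1 (Cohort 2), 2, 4, 8, 12, 16, 20, and 24 predose | 8 | 0 |
| Extension | Weeks 25, 28, 36, 44, 52 | 5 | 0 |
| Total | | 8 + 5 = 13 | 0 |

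3. **Dose in the counted windows.** Under Protocol 6.3 (Tables 2 and 3) and SAP 3.1, the 3 mg arm takes 2 mg from Day 1 to the Week 1 visit. All subjects entering the extension take 2 mg at Week 24. The Day 1 window therefore follows 2 mg or placebo, and the Week 24 window follows 2 mg. In the 3 mg arm, the listed double-blind visits after 3 mg has started are Weeks 2 to 24 predose: 8 − 1 = 7 visits, of which 0 have a count.

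4. **ECG heart rate.** SAP 11.5 counts heart rate below 40 and below 50 bpm at 4 hours after the dose, on the same two days. It does not extend the coverage.

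5. **Holter.** Protocol 10.5.7.5 and Appendices 1 and 2 place Holter recording at Day 1 and Week 1 (Cohort 2), at Weeks 24 and 25, and at any escalation from 2 mg to 3 mg. Its main purpose is heart rate and arrhythmia, and the SAP defers its analysis to a separate plan. It covers the start of 3 mg. It does not measure blood pressure, and apart from escalations it is not scheduled at Weeks 2 to 20 or 28 to 52.

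6. **Planned outputs.** SAP Appendix 3 has four vital sign tables: 14.3.5.1.1 and 14.3.5.1.2 (summaries for each period), and 14.3.5.2 and 14.3.5.3 (cardiac monitoring, full study). None is an abnormality table by its title.

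7. **Declared changes.** SAP Section 12, Table 4, declares four changes: the extension baseline, the FAS, the Per Protocol Set and the OLE FAS. Leaving out the vital sign tabulation is not among them.

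8. **Comparison within the SAP.** The protocol sentence that promised vital sign incidence also promised ECG outliers, and SAP 11.5 implements those. SAP 11.6 and 11.7 set abnormality criteria for lung function and foveal thickness, by visit and at any time after baseline. Section 11.3 has no equivalent, which looks like an omission rather than a decision.

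**The case against.** The strongest defence is that most of the information will still appear somewhere.

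- **Adverse events.** Hypotension, hypertension or bradycardia reported as an adverse event is tabulated by arm, preferred term and maximum severity under SAP 11.1. This is true, but it depends on the investigator's reporting, and both documents list the vital sign endpoint separately from adverse events. SAP 11.4 states the adverse event route for physical examination findings; SAP 11.3 does not state it for vital signs.
- **Minimum, maximum and listing.** SAP 4.4 includes minimum and maximum, so an extreme value would be visible by arm and visit, and every value is listed. That stands, but a minimum does not say how many subjects crossed a limit.
- **Holter.** Heart rate at the start of 3 mg may be fully analysed in the separate SAP. That stands, and it limits the point to what this SAP plans.
- **The 3 mg arm at Week 24.** These subjects take 3 mg up to the visit, so their Week 24 heart rates come about a day after a 3 mg dose. That is correct; the statement here is only that the dose opening the window is 2 mg.
- **Table titles.** SAP Section 4 puts table layouts in a separate document, so the exact content of the second cardiac monitoring table is not known. SAP 11.3, which governs the content, plans nothing further.
- **Visits in the protocol.** Protocol 11.9.1 names only the 4-hour assessments, and only as a possibility. The visit-by-visit commitment comes from the SAP itself.

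A reader might also infer that laboratory severity, listed as "Incidence and severity of laboratory abnormalities and change from Baseline in laboratory", is neglected in the same way because SAP 11.2 relies on tables "describing shifts to abnormality (low or high) will be provided as well". The documents do not support that. SAP 11.2 also grades lymphocyte counts and counts ALT and AST at multiples of the upper limit that include the CTCAE boundaries in Protocol Table 11.

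**Conclusion.** Wrong as written: SAP 11.3 does not implement an endpoint that the SAP itself lists or a tabulation that the protocol promises, and Section 12 does not declare the difference. The incidence part of the endpoint is unreported for blood pressure at every visit. For vital-sign heart rate it is unreported at all 13 listed assessments outside the two 4-hour windows, including the 7 double-blind visits at which the 3 mg arm is on 3 mg.

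Two stronger readings are tempting and do not hold. One is that the endpoint has no analysis: change from baseline is covered, and low heart rate is counted in the monitored windows. The other is that low heart rate on 3 mg, or abnormal blood pressure, is never counted. Holter covers escalation to 3 mg under a plan not seen here, and events reported as adverse events are counted.

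The conclusion assumes that the unseen table layouts add no abnormality counts beyond SAP 11.3, and that dosing follows the schedule.

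**What to change.** Add to SAP 11.3 and Appendix 3 an incidence table of vital sign abnormalities:

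- **Rows:** subjects beyond each limit, by visit and at any time post-baseline. The any-time row should include unscheduled and early termination values.
- **Columns:** double-blind arm for the double-blind period; OLE group for the extension.
- **Limits:** pre-specified before unblinding. The low limits already in Protocol 4.2 and 4.3 (heart rate below 50 bpm, systolic blood pressure below 90 mm Hg, diastolic below 55 mm Hg) can serve, as analysis cut-offs for reporting only. The documents give no high blood pressure cut-offs, and Protocol Appendix 4 has no blood pressure row, so the sponsor must state them.
- **Cross-reference:** point to the Holter SAP for heart rate at escalation to 3 mg.

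If the sponsor prefers not to add the table, SAP Section 12 should declare the omission and give the reason. The cost is one or two tables from data already collected, with no work at the sites.
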